6.5.1 Hypersensitivity

As with any i.v. protein, product allergic type hypersensitivity reactions are possible. Allergic-type hypersensitivity reactions, including anaphylaxis, have been reported as part of the post-marketing experience with ADVATE and have been manifested by dizziness, paresthesias, rash, flushing, face swelling, urticaria, and pruritus. The product contains traces of mouse and hamster proteins. Patients should be informed of the signs of immediate-type hypersensitivity reactions including hives, pruritus, generalized urticaria, angioedema, hypotension (eg, dizziness or syncope), shock and acute respiratory distress (eg, tightness in the chest, wheezing). If these symptoms occur, they should be advised to discontinue use of the product immediately and contact their physicians. In case of anaphylactic shock, the current medical standards for shock treatment should be followed.

Due to the decrease in infusion volume for ADVATE reconstituted in 2 mL SWFI, if hypersensitivity reactions occur there is less time to react by stopping the infusion. Therefore, caution is advised during infusion of ADVATE reconstituted in 2 mL SWFI, especially in children.

6.5.2 Inhibitor Development

The formation of neutralizing antibodies (inhibitors) against FVIII is a known complication in the management of individuals with hemophilia A. These inhibitors are usually IgGs directed against the FVIII procoagulant activity, which are quantified in BU per mL of plasma using the modified Bethesda assay. In patients who develop inhibitors to FVIII, the condition may manifest itself as an insufficient clinical response. In such cases, it is recommended that a specialized hemophilia centre be contacted. The risk of developing inhibitors is correlated to the extent of exposure to FVIII, the risk being highest within the first 20 EDs, and to other genetic and environmental factors. Rarely, inhibitors may develop after the first 100 EDs. Cases of recurrent inhibitor (low titer) have been observed after switching from one FVIII product to another in previously

treated patients with more than 100 EDs who have a history of inhibitor development. Patients treated with coagulation FVIII should be carefully monitored for the development of inhibitors by appropriate clinical observations and laboratory tests.

The formation of inhibitors to FVIII is a known complication in the management of patients with hemophilia A. The risk of developing inhibitors correlates to the extent of prior exposure to FVIII, with the risk being highest within the first 20 EDs. *De novo* inhibitor formation is less commonly observed after 100 EDs.

6.5.3 Injection-Site Reactions/CVAD-Related

For ADVATE reconstituted with 2 mL SWFI, misapplication (intra-arterially or paravenously) may lead to mild, short term injection site reactions, such as bruising and erythema.

If central venous access device (CVAD) is required, risk of CVAD-related complications including local infections, bacteremia and catheter site thrombosis should be considered.

6.5.4 Sodium Content

After reconstitution this medicinal product contains 0.45 mmol sodium (10 mg) per vial. To be taken into consideration by patients on a controlled sodium diet.

6.6 Compliance Statement

This study will be conducted in accordance with this protocol and local and applicable national regulatory requirements. ^{14; 15} Efforts are taken to follow the principles set forth in the International Conference on Harmonization Guideline for Good Clinical Practice E6 (ICH GCP, April 1996) to the extent possible for a non-interventional study.

7. STUDY PURPOSE AND OBJECTIVES

7.1 Study Purpose

The purpose of the study is to collect data on the safety and effectiveness of ADVATE reconstituted in 2 mL SWFI during routine clinical practice. This non-interventional study will be a post-licensure commitment for ADVATE reconstituted in 2 mL SWFI.

7.2 Primary Objective

The primary objective of the study is to assess incidence of all local and general, hypersensitivity and infusion-related reactions, irrespective of product-related causality for the AEs.

7.3 Secondary Objectives

7.3.1 Safety

- To assess incidence of all AEs considered by the investigator to be causally related (possibly or probably related) to ADVATE reconstituted in 2 ml SWFI
- To assess immunogenicity in all subjects
- To assess immunogenicity in PTPs (> 50 EDs) with baseline FVIII \leq 2% and with no history of inhibitors prior to study entry
- To assess immunogenicity in PTPs (> 50 EDs) with baseline FVIII < 1% and with no history of inhibitors prior to study entry

7.3.2 Effectiveness

- To assess effectiveness in on-demand treatment
- To assess effectiveness in prophylaxis
- To assess effectiveness in surgical or dental procedures

7.3.3 Non-clinical Outcomes

- To assess FVIII treatment satisfaction and preference ratings from caregiver
- To assess FVIII infusion volume and time to mix and infuse FVIII treatment

8. STUDY DESIGN

8.1 Overall Study Design

This study is a prospective, non-interventional PASS study that assesses the safety and effectiveness of ADVATE reconstituted in 2 mL SWFI during routine clinical practice. Subjects with severe or moderately severe hemophilia A (FVIII ≤2%) and documented prior exposure to FVIII concentrates, aged ≤12 years, who are prescribed ADVATE and will only receive ADVATE reconstituted in 2 mL SWFI, will be asked to participate. The study will prospectively capture ADVATE related data for 6 months from the date of enrollment. Subjects should receive all FVIII therapy with ADVATE reconstituted in 2 mL SWFI during the study observation period. The investigators shall determine all treatment regimens according to product labeling information and standard practice. For all bleeding episodes requiring treatment, the subject should be treated until adequate hemostasis is achieved. The investigators will also determine all monitoring schedules, including the frequency of clinic visits and laboratory testing. A screening visit during which the investigator determines whether the enrolled subject (ie, one whose legally authorized representative(s) has signed an informed consent form [ICF]) meets all inclusion criteria and none of the exclusion criteria is required. All other study visits, including the last visit, should coincide with the routinely and emergently scheduled

clinic and hospital visits that the subject has in the 6-month period following enrollment. Caregivers will be asked to complete a short survey at the beginning and end of the 6-month observation period. The survey will capture data on their infusion experience and satisfaction with ADVATE reconstituted in 5 mL SWFI at the beginning of the study and with ADVATE reconstituted in 2 mL SWFI at the end of the study. The follow-up survey will also ask caregivers about their preferences between ADVATE reconstituted in 2 mL and 5mL SWFI on a variety of factors. This survey is strictly optional and will only be offered where such a survey is in concordance with non-interventional study regulations and after ethics committee (EC) approval of its use.

8.2 Duration of Study Period(s) and Subject Participation

The overall duration of the study is 42 months from study initiation (ie, first subject enrolled) to study completion (ie, last subject last visit). The recruitment period is expected to be 36 months.

The subject participation period is 6 months from enrollment to subject completion (ie, last study visit), unless prematurely discontinued.

8.3 Outcome Measures

8.3.1 Primary Outcome Measure

The primary outcome measure is the incidence of all local and general, hypersensitivity and infusion-related reactions, irrespective of product-related causality.

8.3.2 Secondary Outcome Measures

8.3.2.1 Safety

- Number and type of AEs considered by the investigator to be causally related (possibly or probably related) to ADVATE reconstituted in 2 mL SWFI
- Number of inhibitors in all subjects
- Number of inhibitors in PTPs (> 50 EDs) with baseline FVIII < 1% and with no history of inhibitors prior to study entry
- Number of inhibitors in PTPs (> 50 EDs) with baseline FVIII ≤ 2% and with no history of inhibitors prior to study entry

8.3.2.2 Effectiveness

• Subjective hemostatic effectiveness rating of excellent, good, fair, or none for each bleeding episode treated

- Number of bleeding episodes treated with 1, 2, 3, ≥ 4 infusions of ADVATE reconstituted in 2 mL SWFI
- Total units of ADVATE reconstituted in 2 mL SWFI administered to treat each bleeding episode
- Overall effectiveness of prophylaxis in subjects who are on a prophylactic regimen, as defined by the investigator, for the full duration of the study
- Global assessment rating of hemostatic effectiveness of ADVATE reconstituted in 2 mL SWFI (excellent, good, fair, or none) in surgical or dental procedures

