6.3 Population to Be Studied

The study population will include 60 evaluable subjects aged \leq 12 years with severe or moderately severe hemophilia A (FVIII \leq 2%) with documented prior exposure to FVIII concentrates. Thirty (30) subjects will be \leq 6 years and the remaining 30 subjects will be \geq 6 to \leq 12 years of age. Of the 30 subjects \leq 6 years of age, at least 15 subjects will be \leq 2 years old. Ongoing enrollment will carefully be monitored to help ensure that the study population reflects the age categories specified.

The targeted enrollment will be 73 subjects. This number was determined to offset the projected dropout rate of 17% experienced in the ADVATE previously untreated patient (PUP) study (060103)^{iii,7}, and to ensure that there are 60 evaluable subjects.

The patient population to be studied (pediatric patients, aged \leq 12 years) is of an age that the participants are not able to provide informed consent. However, appropriate consent procedures will be in place, and the consent of the patient's legally authorized representative(s) will be obtained.

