Study 060103 was a Phase 3b study that investigated the safety and efficacy of ADVATE in 55 PUPs under 6 years of age with severe or moderately severe hemophilia A. vi Of 517 treated bleeding episodes, 90% were managed with 1 or 2 infusions. Hemostatic efficacy was considered excellent or good in 93% of 466 rated bleeding episode treatments. Twenty-seven surgical procedures were performed, with intra- and postoperative hemostatic efficacies considered excellent or good in 22/22 (100%) and 25/25 (100%) of the procedures rated, respectively. Inhibitory antibodies to FVIII developed in 16/55 (29.1%; 95% CI: 17.1%-41.1%) subjects. All the subjects who developed inhibitors had severe hemophilia (FVIII <1%). At the time of inhibitor diagnosis, 7 subjects were categorized with high-titer inhibitors (>5 BU/mL confirmed with a new blood sample) and 9 subjects were categorized with low-titer inhibitors (≤5 BU/mL). An immunogenicity analysis set of 50 subjects was used for the calculation of the odds ratio (OR) of risk factors for inhibitor development, which included all 16 subjects with inhibitors and subjects without inhibitors who had at least 10 EDs. Univariate analysis identified statistically significant OR results for 3 risk factors: family history of inhibitor (4.95 [95% CI: 1.29-19.06]), non-Caucasian ethnicity (4.18, [95% CI: 1.18-14.82]), and intensive treatment at high dose^{vii} within the first 20 EDs (4.50, 95% CI: 1.05-19.25). Intensive treatment at high dose in all but 1 subject, where it was administered for a bleeding episode, consisted of perioperative infusions in the context of port placement. Inhibitor incidence in low-risk subpopulations of subjects who lacked the risk factors confirmed in this study was also examined. While 16/55 (29.1%) subjects in the entire study population developed inhibitors, 7/37 (18.9%) subjects who were Caucasian and 2/25 (8.0%) subjects who were both Caucasian and had no family history developed inhibitors. In the 20 subjects who were Caucasian, had no family history of inhibitors, and did not receive intensive treatment at high dose (lacked all 3 risk factors) there was no inhibitor development (0/20 [0.0%]). No subjects died or withdrew due to AEs. A total of 931 AEs were reported: 46 SAEs and 885 non-serious AEs. All 16 SAEs considered related to the administration of ADVATE were inhibitor development. There were 14 non-serious AEs considered related to the administration of ADVATE; of these, 6 were rated as mild and 8 were rated as moderate.

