8.6.3 Description of Treatment

The treatment regimen, dosing and duration of treatment are at the discretion of the treating physician.

For subject's ≤ 2 years of age, use of the 250 IU size vials is recommended.

Information on treatment is provided in the SmPC as follows:

The posology and duration of the substitution therapy depend on the severity of the FVIII deficiency, on the location and extent of the bleeding and on the patient's clinical condition.

The dose of FVIII is expressed in International Units (IU), which are related to the WHO standard for FVIII products. FVIII activity in plasma is expressed either as a percentage (relative to normal human plasma) or in IUs (relative to the international standard for FVIII in plasma).

One IU of FVIII activity is equivalent to that quantity of FVIII in one mL of normal human plasma. The calculation of the required dose of FVIII is based on the empirical finding that 1 IU FVIII per kg body weight (BW) raises the plasma FVIII activity by 2 IU/dL. The dose is determined using the following formula:

Required units (IU) = BW (kg) x desired FVIII rise (%) x 0.5

In case of the following hemorrhagic events, the FVIII activity should not fall below the given plasma activity level (in % of normal or IU/dL) in the corresponding period. The following table (Table 8.6-1) can be used to guide dosing in bleeding episodes and surgery:

Table 8.6-1 Guide for Dosing in Bleeding Episodes and Surgery			
Degree of Hemorrhage / Type of Surgical Procedure	FVIII Level Required (% or IU/dL)	Frequency of Doses (Hours) / Duration of Therapy (Days)	
Hemorrhage			
Early hemarthrosis, muscle bleeding or oral bleeding.	20 – 40	Repeat injections every 12 to 24 hours (8 to 24 hours for patients under the age of 6) for at least 1 day, until the bleeding episode, as indicated by pain, is resolved or healing is achieved.	
More extensive hemarthrosis, muscle bleeding or hematoma.	30 – 60	Repeat injections every 12 to 24 hours (8 to 24 hours for patients under the age of 6) for 3 – 4 days or more until pain and acute disability are resolved.	
Life threatening hemorrhages.	60 – 100	Repeat injections every 8 to 24 hours (6 to 12 hours for patients under the age of 6) until threat is resolved.	
Surgery			
Minor Including tooth extraction.	30 – 60	Every 24 hours (12 to 24 hours for patients under the age of 6), at least 1 day, until healing is achieved.	

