9. SUBJECT SELECTION, WITHDRAWAL, AND DISCONTINUATION

9.1 Inclusion Criteria

Subjects who meet ALL of the following criteria are eligible for this study:

- Subject has severe or moderately severe hemophilia A (baseline FVIII ≤ 2%)
- Subject is ≤ 12 years of age
- Subject's legally authorized representative(s) has provided written informed consent
- Subject is prescribed ADVATE and will only receive ADVATE reconstituted in 2 mL SWFI
- Documented history of prior exposure to ADVATE (for subjects ≤ 2 years old, at least 3 EDs to ADVATE; for subjects with ≤ 50 EDs, all prior EDs must be to ADVATE; for subjects with >50 EDs, the last 20 prior EDs must be to ADVATE)
- Documented evidence of negative inhibitor test result during ≤10 EDs prior to study entry

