14.3 Handling of Missing, Unused, and Spurious Data

There will be no imputation on any outcome measure in this study. Missing data will be reported as such.

If a subject weight is missing from any infusion record, the subject's last recorded weight will be used to calculate the weight-adjusted dose.

If FVIII activity levels are reported as inequalities, the < or > sign will be dropped for use in numeric analyses.

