14.4.2 Secondary Outcome Measures

Each secondary outcome measure will be calculated by employing the applicable analysis set:

- Number of AEs considered by the investigator to be causally related (possibly or probably related) to ADVATE reconstituted in 2 mL SWFI, SAS
- Number of inhibitors in all subjects, SAS

- Number of inhibitors in PTPs (>50 EDs) with baseline FVIII < 1% and with no history of inhibitors prior to study entry, IAS1
- Number of inhibitors in PTPs (> 50 EDs) with baseline FVIII ≤ 2% and with no history of inhibitors prior to study entry, IAS2
- Subjective hemostatic effectiveness rating of excellent, good, fair, or none for each unique bleeding episode treated, EASBE
- Number of bleeding episodes treated with 1, 2, 3, ≥ 4 infusions of ADVATE reconstituted in 2 mL SWFI, EASBE
- Total units of ADVATE reconstituted in 2 mL SWFI administered to treat each bleeding episode, EASBE
- Overall effectiveness of prophylaxis in subjects who are on a prophylactic regimen for the full duration of the study, EASPT
- Global assessment rating of hemostatic effectiveness of ADVATE reconstituted in 2 mL SWFI (excellent, good, fair, or none) in surgical or dental procedures, EASSDP
- Change in FVIII treatment satisfaction and preference ratings from caregiver between ADVATE reconstituted in 5 mL and 2 mL SWFI, SAS
- Change in FVIII infusion volume and time to mix and infuse FVIII treatment between ADVATE reconstituted in 5 mL and 2 mL SWFI, SAS

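### Total units per bleeding episode is defined only in absolute IU in children from infancy to 12 years, so any summary across ages is substantially confounded with body weight

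*Protocol*

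**What the plan says.** Protocol 8.3.2.2 lists among the effectiveness outcomes "Total units of ADVATE reconstituted in 2 mL SWFI administered to treat each bleeding episode". The synopsis uses the same words. Section 14.4.2 assigns the outcome to the analysis set for bleeding episodes: "Total units of ADVATE reconstituted in 2 mL SWFI administered to treat each bleeding episode, EASBE". None of the three places mentions weight or age.

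Section 8.6.3 gives the dose formula: "Required units (IU) = BW (kg) x desired FVIII rise (%) x 0.5". The population is broad in size. Section 9.1 requires "Subject is ≤ 12 years of age" and sets no lower limit. Section 6.3 plans 30 evaluable children in a younger group (up to 6 years) and 30 in an older group (up to 12). Within the younger group, "at least 15 subjects will be" 2 years old or younger.

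Weight-adjusted dose appears elsewhere in the protocol:

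- Sections 10.3.1 and 10.3.2 collect it for the treatment regimen.
- Section 10.3.3 asks for it in total for surgical and dental procedures.
- Section 14.3 says that when weight is missing from an infusion record, "the subject's last recorded weight will be used to calculate the weight-adjusted dose".

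No listed outcome per bleeding episode uses it.

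**The concern.** Two children with the same kind of bleed, the same target FVIII rise and the same number of infusions receive the same IU/kg but very different total IU if one is an infant and the other is 12. The outcome sits under effectiveness, so a reader will take it as describing how much product is needed to control a bleed. A mean or median across all ages depends partly on the age quotas in 6.3 and on which ages contribute bleeds, neither of which concerns the product. A table by age would show more units in older children even if the response per kilogram were identical.

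The protocol is also uneven with itself: it asks for total weight-adjusted dose for procedures, but only for absolute units for bleeds.

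**Working it through.** **The plan's own figures.** The protocol gives no expected value for units per bleed. Its one planning figure, 73 enrolled for 60 evaluable at 17% dropout, reproduces (60 / 0.83 = 72.3, rounded up to 73) but has no bearing on this point.

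**Step 1: the formula at fixed need.** Take a rise of 40%, the upper end of the first row of Table 8.6-1 ("Early hemarthrosis, muscle bleeding or oral bleeding"), and one infusion, purely as an illustration.

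- IU/kg = 40 x 0.5 = 20 at any weight.
- Total IU = 20 x 10 = 200 at 10 kg, and 20 x 40 = 800 at 40 kg.

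The two weights are assumptions. The fourfold gap in IU is simply the fourfold gap in weight. This shows the direction of the problem, not its share of the real variation, because need is held fixed.

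**Step 2: share of variance, closed form.** Write log(total IU) = log(weight) + log(IU/kg). If the two parts are independent,

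share due to weight = var(log weight) / [var(log weight) + var(log IU/kg)].

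Assume weights log-uniform from 8 to 42 kg. Then var(log weight) = [ln(42/8)]² / 12 = 1.658² / 12 = 0.229.

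| Assumed log-SD of IU/kg | Share due to weight |
|---|---|
| 0.3 | 0.229 / (0.229 + 0.09) = 0.72 |
| 0.4 | 0.229 / (0.229 + 0.16) = 0.59 |
| 0.5 | 0.229 / (0.229 + 0.25) = 0.48 |

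The share is exactly one half when the log-SD of IU/kg is √0.229 = 0.48. The answer therefore turns on how much bleed severity and number of infusions vary.

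**Step 3: share of variance with the protocol's own ranges.** Simulate total IU = weight x rise x 0.5 x number of infusions.

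- Age mix from 6.3: 25% aged 2 or under, 25% aged 2 to 6, 50% aged 6 to 12. One variant has fewer children aged 2 or under.
- Target levels from the three hemorrhage rows of Table 8.6-1: 20 to 40, 30 to 60 and 60 to 100. The mix of bleed types is assumed and varied.
- Number of infusions: about 90% of bleeds with 1 or 2, following the earlier study in children under 6 in 6.4.1 ("Of 517 treated bleeding episodes, 90% were managed with 1 or 2 infusions"). One variant uses 98%.
- Weights (assumption): about 9 kg in infancy to about 40 kg at 12 years, with a 15% spread within age.

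| Result | Base case | Range over scenarios |
|---|---|---|
| Share of log variance due to weight | 43% | 33% to 71% |
| Share of linear variance due to weight | about 23% | 16% to 53% |

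With about 90% of bleeds needing 1 or 2 infusions, the log-scale share is about 33% to 51%. It is clearly above half only if nearly all bleeds need 1 or 2 infusions and severity varies little.

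**Step 4: what a table by age would show (base case).**

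| Age group | Median IU per episode | Median IU/kg per episode |
|---|---|---|
| 2 or under | about 217 | about 20 |
| 2 to 6 | about 337 | about 20 |
| 6 to 12 | about 613 | about 20 |

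The ratio of oldest to youngest is 613 / 217 = 2.8 in IU and about 1 in IU/kg.

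**The case against.** The fallback in 14.3 makes sense only if weight-adjusted dose is to be calculated from infusion records in general. The protocol therefore already foresees IU/kg at infusion level, and a statistical analysis plan, not shown here, may sum it to the episode or tabulate by age. Nothing in 14.4 requires one pooled summary. The hemostatic rating and the number of infusions per bleed are kept as companion outcomes and are not expressed in units. Section 6.4.1 describes bleed treatment in earlier studies by those two measures. Total IU has its own meaning as product consumption. The outcome is secondary and descriptive: the paired tests in 14.4 cover only infusion volume, time and satisfaction, and no decision rests on it.

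Most of this stands, and it limits the consequence. It does not remove the point. The unit of the outcome is fixed in the protocol in three places, so an analysis plan that added IU/kg would still leave absolute IU as the named outcome.

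A reader might infer three stronger things that the documents do not support:

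- *That the outcome mainly measures body size.* The base case gives 43% of log variance, and only some scenarios exceed half.
- *That only the surgical data are weight-adjusted.* Regimen dose is too, and 14.3 implies the same for infusion records.
- *That the result could not be compared with other studies.* The documents report no earlier result in IU or IU/kg per bleed, so they cannot settle this.

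**Conclusion.** The point holds in limited form. As defined, total units per bleeding episode is substantially confounded with body weight: roughly a third to a half of log variance in most scenarios, and up to 71% when severity and infusion number vary little. Median IU differ nearly threefold between the youngest and oldest groups with no difference per kilogram.

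The direction follows from the protocol's own formula and age range. The size rests on assumed body weights and an assumed mix of bleed types, neither of which is in the documents. It also takes doses to follow the formula, while the protocol leaves dosing to the treating physician. The consequence is modest: one secondary descriptive outcome reads less clearly than it could.

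**What to change.** In the synopsis, 8.3.2.2 and 14.4.2, define the outcome as total IU/kg of the 2 mL product per bleeding episode. Use the weight on the infusion record and, where that is missing, the last recorded weight as in 14.3. A different rule, such as the weight nearest in time, would put two weight rules in one protocol and could pick a weight taken after the bleed. Keep total IU per episode as a supportive measure of consumption, preferably shown by the age groups in 6.3.

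The cost is a line of wording in three places and a division by a weight already planned for collection, with no new visit or test. The one drawback is that 10.3.2 collects weight at interval and termination visits only if available, so some weights in growing children may be out of date. Reporting how many episodes relied on the fallback would show how often no weight was on the infusion record. The change concerns only how the outcome is expressed and touches no dose.
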